#### 7.4.2.1.2.5 Specific Guidance for Cytokine Release Syndrome

Cytokine release syndrome is clinically defined and may have various manifestations.

There are no established diagnostic criteria. Signs and symptoms of CRS may include:

- constitutional: fever, rigors, fatigue, malaise
- neurologic: headache, mental status changes, dysphasia, tremors, dysmetria, gait abnormalities, seizure
- respiratory: dyspnea, tachypnea, hypoxemia
- cardiovascular: tachycardia, hypotension
- gastrointestinal: nausea, vomiting, transaminitis, hyperbilirubinemia
- hematology: bleeding, hypofibrinogenemia, elevated D-dimer
- skin: rash

Subjects may be at an increased risk for CRS during the first few days following the initial infusion of AMG 420. Cytokine release syndrome may be life-threatening or fatal. Infusion reactions may be clinically indistinguishable from manifestations of CRS. Throughout the treatment with AMG 420, monitor subjects for clinical signs (eg, fever, tachycardia, dyspnea, tremors) and laboratory changes (eg, transaminase increase) which may be related to CRS.

Grading and management of CRS should be performed according to the guidelines provided in [Table 7-3](#) (based on the adopted grading system referenced in [Lee et al, 2014](#)).

Please also refer to the general guidance for re-start of infusion after interruption due to adverse event in [Section 7.4.2.1.2](#)

For grade 3 and 4 CRS, please also see [Section 7.4.1](#) for DLT considerations.

**Table 7-3. Grading and Management of Cytokine Release Syndrome**

CRS Grade	Description of Severity a	Interruption	Minimum Expected Intervention	Re-Start Guidance	Permanent Discontinuation
1	Symptoms are not life-threatening and require symptomatic treatment only, eg, fever, nausea, fatigue, headache, myalgias, malaise	n/a	Administer symptomatic treatment (eg, paracetamol/acetaminophen for fever). Monitor for CRS symptoms including vital signs and pulse oximetry at least Q2 hours for 12 hours or until resolution, whichever is earlier.	n/a	n/a
2	Symptoms require and respond to moderate intervention 
 
• Oxygen requirement < 40% (for room air, oxygen saturation 90% or less), OR
 
• Hypotension responsive to fluids or low dose of 1 vasopressor, OR
 
• Grade 2 organ toxicity or grade 3 transaminitis per CTCAE criteria
 
	Immediately interrupt AMG 420 until event has improved to CRS grade ≤ 1, but for no less than 72 hours.	Administer: 
 
• Symptomatic treatment (eg, paracetamol/acetaminophen for fever)
 
• Supplemental oxygen when oxygen saturation is < 90% on room air
 
• Intravenous fluids or low dose vasopressor for hypotension when systolic blood pressure is < 85 mmHg. Persistent tachycardia (eg, > 120 bpm) may also indicate the need for intervention for hypotension.
 
 Monitor for CRS symptoms including vital signs and pulse oximetry at least Q2 hours for 12 hours or until resolution to CRS grade ≤ 1, whichever is earlier. Investigators may also use tocilizumab c as an additional therapy in this setting at a dose of 4-8 mg/kg as a single dose, particularly if CRS does not improve to grade ≤ 1 within 4 hours after dose interruption. For subjects with extensive co-morbidities or poor performance status, manage per grade 3 CRS guidance below.	
 
• Re-start possible, if successfully managed and improvement to CRS grade ≤ 1 within 7 days,
 
• Consult with Amgen medical monitor first.
 
• Hospitalization: 48 hours
 
• In the event of 2 consecutive cases of CRS of grade 2, consider reducing dose to 200 µg/day for subjects originally receiving 400 µg/day or 400 µg/day for those originally receiving 600 µg/day
 
• Additional measures: additional assessments and premedication as indicated in Sections 7.4.2.1.2.3/7.4.2.1.2.4
 
	
 
• If there is no improvement to CRS ≤ grade 1 within 7 days
 
• If interruption is > 14 days
 
• In case of repeat grade 2 event despite dose reduction
 

Footnotes defined on last page of table.

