#### **7.4 Dose Modification**

##### **7.4.1 Dose-cohort Study Escalation/De-escalation and Stopping Rules**

The DLT evaluation period (ie, DLT-evaluable period) will be the 4 weeks on AMG 420 treatment within the first treatment cycle, starting on day 1 (start of infusion). The DLT evaluation period may also be extended to assess events starting within the window in case the DLT definition is time dependent.

Treatment in AMG 420 cycle 1 will be considered complete and the subject will be DLT evaluable if the subject has completed the DLT evaluation period or experienced a DLT any time during the DLT evaluation period. A subject will be non-DLT evaluable if he/she drops out before completion of the DLT-evaluable period for reasons other than a

DLT. All available safety data for subjects who are non-DLT-evaluable will still be evaluated and considered in DLRT decisions (see also [Section 10.4.1.1.1.1](#)).

See [Section 5.2.1](#) for description of replacement of subjects.

A DLT will be defined as any of the events described below occurring in a subject during the DLT evaluation period unless clearly attributable to causes other than treatment with AMG 420. The CTCAE version 5.0 (see [Section 12.4](#)) will be used to assess toxicities/adverse events with the exception of CRS and TLS (see [Section 7.4.2.1.2.5](#) and [Section 12.12](#) for grading criteria of CRS and TLS, respectively).

- Death not clearly due to the underlying disease or extraneous causes.

Non-hematologic DLTs:

- Non-hematological adverse event grade 3 or higher, EXCEPT:
  - infection responding to antibiotic/anti-infective treatment within 48 hours
  - grade 3 fatigue or asthenia
  - grade 3 headache resolving to  $\leq$  grade 2 within 72 hours
  - grade 3 insomnia resolving to  $\leq$  grade 2 within 7 days
  - grade 3 fever resolving to  $\leq$  grade 2 within 72 hours
  - grade 3 nausea, vomiting, or diarrhea responding if successfully managed with optimal medical support and resolved within 72 hours
  - laboratory parameters of grade  $\geq$  3, not considered clinically relevant, and improved to grade  $\leq$  2 within 72 hours

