**Table 7-3. Grading and Management of Cytokine Release Syndrome**

CRS Grade	Description of Severity a	Interruption	Minimum Expected Intervention	Re-Start Guidance	Permanent Discontinuation
3	Symptoms require and respond to aggressive intervention 
 
• Oxygen requirement <math>\geq 40\%</math>, OR
 
• Hypotension requiring high doseb or multiple vasopressors, OR
 
• Grade 3 organ toxicity or grade 4 transaminitis per CTCAE criteria
 
	Immediately interrupt/delay AMG 420 until event has improved to CRS grade $\leq 1$ .	Admit to intensive care unit for close clinical and vital sign monitoring per institutional guidelines. Administer dexamethasone (or equivalent) IV at a dose maximum of 3 doses of 8 mg (24 mg/day). The dose should then be reduced step-wise. AND/OR Investigators should also consider use of tocilizumab c as an additional therapy in this setting at a dose of 4-8 mg/kg as a single dose.	As for CRS grade 2	
 
• If there is no improvement to CRS <math>\leq</math> grade 2 within 5 days and CRS <math>\leq</math> grade 1 within 7 days.
 
• In case of 2 separate grade 3 CRS events.
 
• If interruption is <math>> 14</math> days
 

4	Life-threatening symptoms 
 
• Requirement for ventilator support OR
 
• Grade 4 organ toxicity (excluding transaminitis) per CTCAE criteria
 
	n/a	Admit to intensive care unit for close clinical and vital sign monitoring per institutional guidelines. Administer dexamethasone (or equivalent) IV at a dose maximum of 3 doses of 8 mg (24 mg/day). Further corticosteroid use should be discussed with the Amgen medical monitor. Additionally, tocilizumab c should be administered at a dose of 4-8 mg/kg as a	n/a	Immediately stop the infusion (if applicable) and permanently discontinue AMG 420 therapy.

			single dose and may be repeated once within 24 to 48 hours based on clinical assessment.		
--	--	--	--	--	--

Footnotes defined on next page

CRS = cytokine release syndrome; CTCAE = Common Terminology Criteria for Adverse Events; IV = intravenous

a Revised grading system for cytokine release syndrome ([Lee et al, 2014](#))

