b High dose vasopressors (all doses are required for  $\geq 3$  hours): norepinephrine monotherapy  $\geq 20 \mu\text{g}/\text{min}$ , dopamine monotherapy  $\geq 10 \mu\text{g}/\text{kg}/\text{min}$ , phenylephrine monotherapy  $\geq 200 \mu\text{g}/\text{min}$ , epinephrine monotherapy  $\geq 10 \mu\text{g}/\text{min}$ ; if on vasopressin, vasopressin + norepinephrine equivalent of  $\geq 10 \mu\text{g}/\text{min}$ ; if on combination vasopressors (not vasopressin), norepinephrine equivalent of  $\geq 20 \mu\text{g}/\text{min}$ .

c All sites will ensure that CRS rescue medications are available on-site, including corticosteroids and (for sites in regions where tocilizumab is approved and available, eg, the US and Germany) 2 doses of tocilizumab per study subject.

#### 7.4.2.1.3 Permanent Discontinuation of AMG 420

AMG 420 treatment will be permanently discontinued in the event of:

- infusion-related reaction grade 4 (the infusion has to be stopped immediately)
- grade 4 CRS
- grade 2 or 3 CRS meeting any of the criteria listed below:
  - grade 2 or 3 CRS that does not improve to  $\leq$  grade 1 within 7 days
  - grade 3 CRS that does not improve to  $\leq$  grade 2 within 5 days
  - if a subject experiences 2 separate grade 3 CRS events
  - if a subject experiences repeat grade 2 CRS event after dose reduction
  - grade 3 CRS at the initial run-in dose of the first treatment cycle if a dose step is being used
- grade 3 or higher TLS
- neurologic events considered related to AMG 420 by the investigator and meeting one or more of the following criteria:
  - grade 3 neurologic event leading to treatment interruption and has not resolved to  $\leq$  grade 1 within 14 days despite infusion interruption
  - grade 3 neurologic event that recurs after dose reduction
  - grade 4 neurologic event
- DLT or other unmanageable toxicity unless a subject has a clear clinical benefit from treatment, the toxicity has resolved to  $\leq$  grade 1 or baseline and after consultation with the sponsor
- in case of re-appearance of the same grade 4 adverse event
- treatment interruption of more than 2 weeks or several interruptions exceeding a total of 14 days of treatment per cycle due to serious adverse events/adverse events
- possible DILI requiring permanent withholding as per [Section 7.4.3](#)
- non-manageable GvHD
- subjects who require more than 1 dose reduction
- disease progression as defined by revised IMWG response criteria

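### Table 7-3 sets a 72-hour minimum hold after grade 2 CRS but none after grade 3 CRS, so from cycle 2 onward the more severe event may be restarted sooner

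*Protocol*

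**What the plan says.** Table 7-3 in Section 7.4.2.1.2.5 of the protocol manages CRS by grade, with separate columns for interruption, intervention, restart and permanent discontinuation.

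- **Grade 2, Interruption:** "Immediately interrupt AMG 420 until event has improved to CRS grade ≤ 1, but for no less than 72 hours". There are two conditions, and both must be met.
- **Grade 3, Interruption:** "Immediately interrupt/delay AMG 420 until event has improved to CRS grade" 1 or lower. There is one condition and no minimum time.
- **Grade 3, Re-Start Guidance:** "As for CRS grade 2". The grade 2 Re-Start cell allows restart if the event is successfully managed and improves to grade 1 or lower within 7 days. It adds "Consult with Amgen medical monitor first", 48 hours of hospitalization, a possible dose reduction after two consecutive grade 2 events, and extra assessments and premedication.
- **Grade 2, Minimum Expected Intervention:** "For subjects with extensive co-morbidities or poor performance status, manage per grade 3 CRS guidance below".

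Two other sections limit when a grade 3 event can be restarted at all. Section 7.4.1 defines the dose-limiting toxicity (DLT) window: "The DLT evaluation period (ie, DLT-evaluable period) will be the 4 weeks on AMG 420 treatment within the first treatment cycle". Section 7.4.2.1.3 lists as a reason for permanent discontinuation "DLT or other unmanageable toxicity unless a subject has a clear clinical benefit from treatment", subject to resolution and sponsor consultation. It separately lists "grade 3 CRS at the initial run-in dose of the first treatment cycle if a dose step is being used".

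**The concern.** A minimum hold should not become weaker as the event becomes more severe. Here the fixed 72-hour wait protects the subject with grade 2 CRS and not the subject with grade 3 CRS, for whom the timing of re-infusion is left to case-by-case consultation.

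Elsewhere the protocol works the other way. In Table 7-1, a grade 3 infusion-related reaction follows the grade 2 restart rules with a mandatory dose reduction added. For CRS, a first grade 3 event carries neither a time floor nor a mandatory reduction, and Section 7.4.2.1.2.4 permits restart at the same dose.

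What is at stake is subject safety under the dosing rules. Table 3-1 names CRS as the only important identified risk, and Section 7.4.2.1.2.5 warns that it can be fatal. No effect on the planned safety tables is claimed.

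**Working it through.** The plan states no figure to reproduce. The check is a comparison of text, followed by simple arithmetic on its size.

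**1. Is there a floor for grade 3 anywhere?**

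| Place | Time rule | Floor before a grade 3 restart? |
|---|---|---|
| Table 7-3, grade 2 Interruption | at least 72 h | No; grade 3 has its own Interruption text |
| Table 7-3, grade 3 Interruption | improvement to grade 1 or lower | No |
| Table 7-3, grade 2 Re-Start (inherited by grade 3) | improvement within 7 days | No; this is an upper limit |
| Section 7.4.2.1.2.1 | 14-day interruption limit | No; this is an upper limit |
| Section 7.4.2.1.2.3 | 48 h in hospital | No; it runs after restart |
| Section 7.4.2.1.3 | 5-, 7- and 14-day limits | No; these are upper limits |

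The cross-reference to grade 2 sits in the Re-Start column and points to a cell without the 72 hours.

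**2. When can a grade 3 event be restarted?**

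- In cycle 1, grade 3 CRS is a non-hematologic event of grade 3 or higher and is not among the exceptions in Section 7.4.1. It is therefore a DLT unless clearly due to another cause, and by default ends treatment. At the run-in dose of a dose step it is a named discontinuation trigger.
- From cycle 2 onward the DLT window has closed. A first grade 3 event that improves to grade 2 or lower within 5 days and grade 1 or lower within 7 days may be restarted.
- A cycle 1 subject kept on treatment under the clinical-benefit exception is in the same position.

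**3. Earliest restart as written.** Let *t* be the hours to grade 1 or lower.

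- Grade 2: max(*t*, 72).
- Grade 3: *t*, after medical monitor consultation.
- For *t* < 72, grade 3 may restart 72 − *t* hours sooner. With *t* = 24 the difference is 48 hours; with *t* = 48 it is 24 hours. These values of *t* are assumed, because the documents give no CRS recovery times.

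**4. How many subjects?** Section 3.2.2.4 reports 12 CRS events in the first-in-human study: 10 in cycle 1 and 2 in cycle 2, the latter both grade 1. All CRS below 800 µg/day was grade 1. About 20 subjects are planned here.

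**5. Cost of a 72-hour floor.** One infusion period is 28 × 24 = 672 hours, and 72/672 = 10.7%. Three days is 3/14 = 21% of the 14-day limit.

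**The case against.** The strongest reply is that the case is remote. It needs grade 3 CRS, from cycle 2 onward or under the cycle 1 exception, as the subject's first grade 3 event, and settling in under 72 hours. The first-in-human data contain no such case, and CRS below 800 µg/day was all grade 1. This stands as a limit on size, with two reservations: that grading used CTCAE and not the Table 7-3 scale, and 600 µg/day was not tested in that study (Section 5.4).

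Second, the cross-reference to grade 2 could be read as carrying over the 72 hours. That may be the intent, but the column it sits in does not say so. If it is the intent, the edit simply records it.

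Third, a grade 3 event brings ICU admission, dexamethasone with stepwise reduction and/or tocilizumab, monitor consultation and 48 hours in hospital after restart, and a second grade 3 event ends treatment. These make a very early restart less likely. None of them is a time floor, and the table does not require the steroid reduction to finish first. Consultation also applies to grade 2, where the sponsor still set a fixed minimum.

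Fourth, the sentence sending frailer grade 2 subjects to the grade 3 guidance is in the Intervention column, so by the same column reading they keep the 72 hours. That is a fair reading; the table simply does not say.

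Finally, Amendment 5 records that the program has been terminated, which reduces the practical benefit. The same amendment nonetheless added management rules for subjects still on treatment.

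**Conclusion.** The concern holds. As written, the minimum hold after CRS is inverted by grade. The conclusion rests on reading each column of Table 7-3 as written and on finding no floor in Sections 7.4.1 or 7.4.2.1.2.1 to 7.4.2.1.3.

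Its reach is narrow: first grade 3 events from cycle 2 onward, and cycle 1 subjects retained for clinical benefit. Within that group the restart may come up to 72 hours sooner than after grade 2, depending on a recovery time that the documents do not give. Few subjects should be affected, and no endpoint or analysis depends on the point. It should be corrected because it concerns the product's main known risk and is easily put right.

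**What to change.** In the grade 3 Interruption cell of Table 7-3, add after the improvement condition: *but for no less than 72 hours*. This also removes the doubt about grade 2 subjects managed under the grade 3 guidance, since both rows would then carry the same minimum.

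The text change is one phrase, made through a protocol amendment with ethics committee submission. For an affected subject the loss is at most 72 hours of infusion in one cycle. On its own this would not force discontinuation under the 14-day rule. The documents give no rationale for 72 hours, so the change secures consistency between grades; it does not show that 72 hours is the right duration for grade 3.

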**Table 7-3. Grading and Management of Cytokine Release Syndrome**

CRS Grade	Description of Severity a	Interruption	Minimum Expected Intervention	Re-Start Guidance	Permanent Discontinuation
3	Symptoms require and respond to aggressive intervention 
 
• Oxygen requirement <math>\geq 40\%</math>, OR
 
• Hypotension requiring high doseb or multiple vasopressors, OR
 
• Grade 3 organ toxicity or grade 4 transaminitis per CTCAE criteria
 
	Immediately interrupt/delay AMG 420 until event has improved to CRS grade $\leq 1$ .	Admit to intensive care unit for close clinical and vital sign monitoring per institutional guidelines. Administer dexamethasone (or equivalent) IV at a dose maximum of 3 doses of 8 mg (24 mg/day). The dose should then be reduced step-wise. AND/OR Investigators should also consider use of tocilizumab c as an additional therapy in this setting at a dose of 4-8 mg/kg as a single dose.	As for CRS grade 2	
 
• If there is no improvement to CRS <math>\leq</math> grade 2 within 5 days and CRS <math>\leq</math> grade 1 within 7 days.
 
• In case of 2 separate grade 3 CRS events.
 
• If interruption is <math>> 14</math> days
 

4	Life-threatening symptoms 
 
• Requirement for ventilator support OR
 
• Grade 4 organ toxicity (excluding transaminitis) per CTCAE criteria
 
	n/a	Admit to intensive care unit for close clinical and vital sign monitoring per institutional guidelines. Administer dexamethasone (or equivalent) IV at a dose maximum of 3 doses of 8 mg (24 mg/day). Further corticosteroid use should be discussed with the Amgen medical monitor. Additionally, tocilizumab c should be administered at a dose of 4-8 mg/kg as a	n/a	Immediately stop the infusion (if applicable) and permanently discontinue AMG 420 therapy.

			single dose and may be repeated once within 24 to 48 hours based on clinical assessment.		
--	--	--	--	--	--

Footnotes defined on next page

CRS = cytokine release syndrome; CTCAE = Common Terminology Criteria for Adverse Events; IV = intravenous

a Revised grading system for cytokine release syndrome ([Lee et al, 2014](#))

b High dose vasopressors (all doses are required for  $\geq 3$  hours): norepinephrine monotherapy  $\geq 20 \mu\text{g}/\text{min}$ , dopamine monotherapy  $\geq 10 \mu\text{g}/\text{kg}/\text{min}$ , phenylephrine monotherapy  $\geq 200 \mu\text{g}/\text{min}$ , epinephrine monotherapy  $\geq 10 \mu\text{g}/\text{min}$ ; if on vasopressin, vasopressin + norepinephrine equivalent of  $\geq 10 \mu\text{g}/\text{min}$ ; if on combination vasopressors (not vasopressin), norepinephrine equivalent of  $\geq 20 \mu\text{g}/\text{min}$ .

c All sites will ensure that CRS rescue medications are available on-site, including corticosteroids and (for sites in regions where tocilizumab is approved and available, eg, the US and Germany) 2 doses of tocilizumab per study subject.

#### 7.4.2.1.3 Permanent Discontinuation of AMG 420

AMG 420 treatment will be permanently discontinued in the event of:

- infusion-related reaction grade 4 (the infusion has to be stopped immediately)
- grade 4 CRS
- grade 2 or 3 CRS meeting any of the criteria listed below:
  - grade 2 or 3 CRS that does not improve to  $\leq$  grade 1 within 7 days
  - grade 3 CRS that does not improve to  $\leq$  grade 2 within 5 days
  - if a subject experiences 2 separate grade 3 CRS events
  - if a subject experiences repeat grade 2 CRS event after dose reduction
  - grade 3 CRS at the initial run-in dose of the first treatment cycle if a dose step is being used
- grade 3 or higher TLS
- neurologic events considered related to AMG 420 by the investigator and meeting one or more of the following criteria:
  - grade 3 neurologic event leading to treatment interruption and has not resolved to  $\leq$  grade 1 within 14 days despite infusion interruption
  - grade 3 neurologic event that recurs after dose reduction
  - grade 4 neurologic event
- DLT or other unmanageable toxicity unless a subject has a clear clinical benefit from treatment, the toxicity has resolved to  $\leq$  grade 1 or baseline and after consultation with the sponsor
- in case of re-appearance of the same grade 4 adverse event
- treatment interruption of more than 2 weeks or several interruptions exceeding a total of 14 days of treatment per cycle due to serious adverse events/adverse events
- possible DILI requiring permanent withholding as per [Section 7.4.3](#)
- non-manageable GvHD
- subjects who require more than 1 dose reduction
- disease progression as defined by revised IMWG response criteria
- relapse of disease subsequent to response (stringent CR, CR, very good PR, or PR) on protocol treatment.
- occurrence or progression of a medical condition which in the opinion of the investigator should preclude further participation of the subject in the study
- administration of relevant non-permitted concomitant medications
- requirement for alternative therapy
- subject's request

- subject or investigator not compliant with the study protocol
- Women who become pregnant or breastfeed while on treatment (see [Section 12.5](#) for pregnancy and lactation cases reporting requirements)

For grading of events, refer to [Section 9.2.3.1](#).

All reasons for treatment discontinuation should be clearly and comprehensively documented in the eCRF. If a subject has not continued to present for study visits, the investigator should determine the reason and circumstances as completely and accurately as possible.

In any case of premature treatment discontinuation, the investigator should make every effort to perform all examinations scheduled for the end of treatment (EOT).

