#### Delay of Subsequent Infusion due to Adverse Events

Events occurring after the end of the infusion and requiring a delay of treatment will be managed by delay of the subsequent infusion. The site should record any delay of an infusion on the eCRF and provide the start and stop date/time of the infusion.

Events requiring a delay of the subsequent infusion are listed in [Table 7-1](#). Infusion interruptions or delays **greater than 7 days** for other reasons need to be discussed with the Amgen Medical Monitor. **Delays of treatment cycles beyond 14 days are not permitted.**

Events requiring an infusion interruption including guidance for management, re-start, and permanent discontinuation are listed in [Table 7-1](#) and [Table 7-3](#).

---

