#### 7.4.2.1.2.4 Dosage Adjustments/Re-Start at a Lower Dose Level/ Dose-Escalation

For adverse events for which re-start of treatment is allowed according to the guidelines outlined in [Table 7-1](#) and [Table 7-3](#), treatment may be resumed under medical supervision at the same dose or a lower dose.

Premedication as described in [Section 7.1.4](#) must be administered prior to re-start, if applicable.

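### The grade 3 CRS row of Table 7-3 omits the run-in-dose stop that Section 7.4.2.1.3 requires, so a site using the table alone could restart a subject who must stop

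*Protocol*

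**What the plan says.** Section 7.4.2.1.3 of the protocol is a mandatory list of reasons for stopping AMG 420 permanently. Under grade 2 or 3 CRS it gives five criteria. The fifth is "grade 3 CRS at the initial run-in dose of the first treatment cycle if a dose step is being used", and it carries no exception.

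Table 7-3 has its own column for permanent discontinuation. In the grade 3 row that column lists three items: too slow an improvement (5-day and 7-day limits), a recurrence ("In case of 2 separate grade 3 CRS events"), and an interruption of more than 14 days. The re-start cell in the same row reads "As for CRS grade 2". The grade 2 cell permits a restart if the event is managed and improves to grade 1 or lower within 7 days, with the condition "Consult with Amgen medical monitor first". Neither the grade 3 row nor footnotes a to c mention the run-in dose or Section 7.4.2.1.3.

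Several places make the table the working source:

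- The CRS entry in Table 7-1 refers to Table 7-3 for grading, stopping and rechallenge.
- Section 7.4.2.1.2.2 states: "Events requiring an infusion interruption including guidance for management, re-start, and permanent discontinuation are listed in" Tables 7-1 and 7-3.
- Section 7.4.2.1.2.4 uses the same two tables to decide whether a restart is allowed: "For adverse events for which re-start of treatment is allowed according to the guidelines outlined in" them, "treatment may be resumed under medical supervision at the same dose or a lower dose".

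**The concern.** The table has a discontinuation column, is named as the source of the CRS stopping rules, and repeats the other CRS criteria of Section 7.4.2.1.3. A reader can reasonably take it as complete. For a first grade 3 CRS at the run-in dose it is not only silent on the stop: its re-start cell points to a restart.

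What is at stake is re-exposure after an event for which the same row requires intensive-care admission. The re-start guidance also does not fit the situation. Section 7.4.2.1.2.4 gives 400 µg/day as the lower dose for subjects assigned 600 µg/day, which is above the 200 µg/day at which a run-in event would have occurred. The point concerns subject safety and consistency of conduct; it does not touch an estimate or a test.

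**Working it through.** No figure in the plan needs to be reproduced, so the check is a comparison of the two texts.

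**1. Criteria in Section 7.4.2.1.3 for grade 2 or 3 CRS, looked up in Table 7-3**

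| Criterion in Section 7.4.2.1.3 | In Table 7-3? |
|---|---|
| Grade 2 or 3, not down to grade 1 or lower within 7 days | Yes, grade 2 and grade 3 rows |
| Grade 3, not down to grade 2 or lower within 5 days | Yes, grade 3 row, combined with the 7-day limit |
| Two separate grade 3 events | Yes, grade 3 row |
| Repeat grade 2 after dose reduction | Yes, grade 2 row ("In case of repeat grade 2 event despite dose reduction") |
| Grade 3 at the cycle 1 run-in dose when a dose step is used | **No** |

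Four of five are present and one is missing. If the criterion that applies only to grade 2 is set aside, three of four are present and the same one is missing.

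**2. A case that separates the texts.** A cohort 2 subject has a first grade 3 CRS on day 1 at 200 µg/day and is at grade 1 by day 4. The improvement is inside the 5-day and 7-day limits, there has been one grade 3 event, and the interruption is under 14 days. Under Table 7-3 a restart is possible after consulting the medical monitor. Under Section 7.4.2.1.3 treatment ends.

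**3. Do the cross-references close the gap?** Section 7.4.2.1.2.5, which introduces Table 7-3, points to Section 7.4.2.1.2 for restarts and, for grade 3 and 4 CRS, to Section 7.4.1. The run-in stop is in neither. Section 7.4.1 defines DLTs but does not say when an individual subject must stop treatment.

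**4. Does the DLT rule replace the run-in stop?** Grade 3 CRS in cycle 1 would normally be a DLT: it is a grade 3 non-hematologic event and CRS is not among the exceptions in Section 7.4.1. Section 7.4.2.1.3 stops treatment for a DLT, but with an exception when there is clear clinical benefit, the toxicity has resolved to grade 1 or baseline, and the sponsor has been consulted. That exception has little room here. The run-in ends on day 3 (Section 7.1.1.2) and an interruption of more than 14 days forces discontinuation (Table 7-3), so the latest restart is about day 3 + 14 = 17. As far as its layout can be read, Table 12-4 schedules no M-protein or free light chain test between pre-dose and the end of cycle 1. The DLT rule is therefore a strong backstop, but not the same rule.

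**5. Reach.** Section 7.1.1.2 gives every cohort 2 subject a run-in dose: about 10 subjects. If the dose level review team adopts a step in cohort 1 as well, the number is about 10 + 10 = 20. Only events on days 1 to 3 count. Section 3.2.2.4 reports that all first-in-human CRS below 800 µg/day was grade 1, although graded by CTCAE and not on the Table 7-3 scale.

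**The case against.** The strongest reply is that the protocol gives only one answer. Section 7.4.2.1.3 is mandatory, stands directly after the table, and is titled for exactly this purpose; the wording that allows a restart is permissive and cannot override it. Section 7.4.2.1.2.1 also refers to the instructions in the text and not only to the tables. Table 7-3 omits other general stops too, such as the DLT stop and the limit of one dose reduction, so it need not be read as exhaustive. A wrong restart would mean overlooking two stopping rules. It would also have to pass several safeguards: the six-day hospital stay for dose-step subjects, intensive-care admission, consultation with the medical monitor, and at least 48 hours in hospital after a restart. Finally, the rationale for Amendment 5 cites termination of the program and no further drug supply, so perhaps no further subject will receive a run-in dose.

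Most of this stands. The mismatch is an omission and not a contradiction: a reader who applies both texts stops treatment. The safeguards make an error unlikely. They do not correct the table. The run-in stop is specific to CRS, the other CRS criteria are repeated, and the re-start cell for this event gives the wrong action in the place to which sites are directed.

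**Conclusion.** The concern holds, as a minor point. One of the five grade 2 or 3 CRS stopping criteria is missing from Table 7-3, and the grade 3 re-start cell permits what Section 7.4.2.1.3 forbids.

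The omission itself is certain from the text. Harm depends on a site using the table without the section that follows it, and on the medical monitor and the DLT rule both failing to catch the case. The documents give no basis for a probability of that. The exposed group is about 10 to 20 subjects for three days each, and they do not show whether anyone else would start a run-in dose after Amendment 5. No endpoint, sample size or planned analysis is affected.

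**What to change.** Keep the stricter rule and align the grade 3 row of Table 7-3 with it:

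- **Permanent Discontinuation:** add *grade 3 CRS at the initial run-in dose of cycle 1 when a dose step is used; see also Section 7.4.2.1.3 (including the DLT rule)*.
- **Re-Start Guidance:** change to *as for CRS grade 2, except do not restart if the event occurred at the run-in dose*.

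The cost is two cells in one table row. It needs no new clinical decision, because the sponsor has already chosen the rule, and it changes nothing in data collection, sample size or analysis. It is worth making if any further subject could start a run-in dose, or if the table is reused in another protocol.
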